6.3 Other Regorafenib-Related Grade 3 or 4 Non-Hematologic Toxicities

The dose reduction guidelines for non-hematologic toxicities are shown in Table 6. If a Grade 3 non-hematologic toxicity that is expected to be manageable and reversible with dose reduction occurs, treatment with regorafenib should be held until the toxicity resolves to \leq Grade 1. If the Grade 3 non-hematologic toxicity lasts longer than 7 days, study drug will be discontinued. Patients with Grade 3 non-hematologic toxicity lasting \geq 7 days that does not resolve to \leq Grade 1 within 3 weeks should also be removed from the study, unless the treating physician and the Medical Monitor agree that continued treatment at lower doses is in the best interest of the patient. If a Grade 4 non-hematologic toxicity occurs, study drug will be discontinued.

If Grade 3 or 4 non-hematologic toxicity other than nausea, vomiting, or alopecia occurs, treatment with regorafenib should be held, and should be resumed at 1-level dose reduction(s) (see Table 1) as soon as the toxicity resolves to \leq Grade 1. Dose reductions will also apply for nausea and vomiting if the toxicity is Grade 3 or 4 and persists for 7 days after maximal antiemetic prophylaxis.

Table 6 Dose Modifications for Regorafenib Non-Hematologic Toxicities

Toxicity	Regorafenib Dose ^a
Grade 1 and Grade 2	No dose modifications ^a .
Grade 3 ^b	Hold dose until recovery to \leq Grade 2 (for AEs in Cycle 1: resolution to \leq Grade 1), then resume regorafenib at one lower dose level. For AEs occurring in Cycle 2 or later the investigator may consider a retreatment at the dose Level 0. If subject experiences a second Grade 3 toxicity, withhold dose until toxicity is \leq Grade 2, then reduce 1 dose level and resume treatment.
Grade 4 ^b	Discontinue treatment. For certain toxicities such as laboratory assessments (e.g., lipase increase without signs of a clinical pancreatitis), a decision about the further continuation and dose of treatment has to be determined after discussion between investigator and the sponsor.

^aThe investigator may consider lowering the regorafenib dose level in the case of Grade 1-2 toxicities which interfere with the activities of daily life, such as long lasting fatigue, anorexia, etc.

^bSubjects who develop Grade 3 hyperlipasemia or hyperamylasemia without clinical or other evidence of pancreatitis, or Grade 3/Grade 4 hypophosphatemia may continue study treatment without interruption if this is deemed medically acceptable by the investigator. Relevant diagnostic measures to exclude other adverse events leading to hyperlipasemia, hyperamylasemia, or hypophosphatemia will be mandatory before dosing of regorafenib is continued.

CONFIDENTIAL

STUDY DEVICE: SIR-Spheres®

SCRI INNOVATIONS STUDY NUMBER: GI 189

DATE OF ORIGINAL PROTOCOL: 16 December 2013

Date of Amendment #1: 15 April 2014

Version 2.0

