6. DOSE MODIFICATIONS

If toxicity occurs, the toxicity will be graded utilizing the NCI CTCAE v4.0, and appropriate supportive care treatment will be administered to decrease the signs and symptoms thereof. Dose adjustments will be based on the organ system exhibiting the greatest degree of toxicity.

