6.2 Regorafenib Dose Modifications for Non-Hematologic Toxicity

6.2.1 Regorafenib Dose Modifications for Abnormal Liver Function Tests

Regorafenib has been associated with severe drug-induced liver injury with fatal outcome in previous studies. Liver function tests (LFTs) will be monitored during study treatment as described in **Error! Reference source not found.** Appendix A and **Error! Reference source not found.** Appendix B. Dose modifications for regorafenib are recorded in Table 3 below.

Table 3 Regorafenib Dose Modifications for Abnormal Liver Function Tests

Toxicity	Regorafenib Dose
Baseline - Grade 1 And Recurrence OR Baseline Grade 1 – Grade 2 And Recurrence	Treat on time and check AST, ALT and bilirubin 2x/week for 2 weeks followed by weekly assessments for at least 4 weeks.
Baseline - Grade 2	Hold dose until \leq Grade 1 and check AST, ALT and bilirubin 2x/week. Resume regorafenib at 1 lower dose level and check AST, ALT, bilirubin 2x/week for 2 weeks followed by weekly assessments for at least 4 weeks. ^a
Recurrence of Baseline - Grade 2	Discontinue regorafenib ^b .
Baseline Any Grade-Grade 3	Hold dose until \leq Grade 1 for baseline - Grade 1 OR until Grade 2 if baseline was Grade 2.

CONFIDENTIAL

STUDY DEVICE: SIR-Spheres®

SCRI INNOVATIONS STUDY NUMBER: GI 189

DATE OF ORIGINAL PROTOCOL: 16 December 2013

Version 2.0

Date of Amendment #1: 15 April 2014

	Check AST, ALT and bilirubin 2x/week.
	Resume regorafenib at 1 lower dose level and check AST, ALT, bilirubin 2x/week for 2 weeks followed by weekly assessments for at least 4 weeks. ^a
	Note: If ALT or AST >8 x ULN with a concomitant rise in bilirubin (of any degree) compared to previous bilirubin values, consider permanent discontinuation at the first occurrence ^b .
Recurrence of Baseline Any Grade-Grade 3	Discontinue regorafenib ^b .
Baseline Any Grade-Grade 4	Discontinue regorafenib ^b

^a If all values remain stable for 2 full cycles, dose re-escalation may be considered at the discretion of the investigator. After re-escalation AST, ALT, and bilirubin should be checked 2x/week for 2 weeks, followed by weekly assessments for at least 4 weeks.

^b In case of discontinuation, AST, ALT, and bilirubin should be checked 2x/week for 2 weeks, followed by weekly assessments until recovery to baseline.

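### For other non-hematologic toxicities, Protocol Section 6.3 both stops regorafenib after a Grade 4 event and tells the site to restart it one dose level lower

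*Protocol*

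**What the plan says.** Section 6.3 opens by pointing to Table 6 for the dose-reduction guidelines. Three instructions on Grade 4 events follow.

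- **Paragraph 1:** "If a Grade 4 non-hematologic toxicity occurs, study drug will be discontinued". It gives no exception.
- **Paragraph 2:** "If Grade 3 or 4 non-hematologic toxicity other than nausea, vomiting, or alopecia occurs, treatment with regorafenib should be held, and should be resumed" one dose level lower as soon as the event is Grade 1 or less. Nausea and vomiting have their own sentence: "Dose reductions will also apply for nausea and vomiting if the toxicity is Grade 3 or 4 and persists for 7 days" despite maximal antiemetic prophylaxis.
- **Table 6, Grade 4 row:** "Discontinue treatment. For certain toxicities such as laboratory assessments (e.g., lipase increase without signs of a clinical pancreatitis"), with those cases decided between investigator and sponsor. Footnote b adds that patients with certain Grade 3 enzyme rises "or Grade 3/Grade 4 hypophosphatemia may continue study treatment without interruption if this is deemed medically acceptable by the investigator".

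For Grade 3 events, paragraph 1 holds drug until Grade 1 or less where the event is expected to be manageable and reversible. It stops drug if the event lasts more than 7 days. It then removes patients whose event of 7 days or more has not resolved to Grade 1 or less within 3 weeks, unless the treating physician and Medical Monitor agree to continue at a lower dose. Table 6 requires Grade 1 or less in Cycle 1 but accepts Grade 2 or less afterwards. It restarts one level lower, lets the investigator consider Level 0 from Cycle 2, and sets no time limit.

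**The concern.** Paragraphs 1 and 2 give opposite directions for the same patient. A clinical Grade 4 event that has resolved is a permanent stop under one and a restart under the other. This is a dosing instruction after the most severe non-fatal grade of toxicity, in a trial whose primary objective is safety, so it should not depend on which paragraph the site reads.

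The Grade 3 wording is a lesser problem of the same kind: sites could differ on how long to wait and on how far the event must recover before restarting. The SAP's descriptive tables of regorafenib modifications and treatment discontinuations, with reasons, would then pool patients managed under different rules.

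**Working it through.** No arithmetic applies beyond counting days, so the check is to run example patients through each instruction.

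| Example patient | Paragraph 1 | Paragraph 2 | Table 6 |
|---|---|---|---|
| Clinical Grade 4 event outside the Table 6 exceptions, resolved to Grade 1 | Stop | Restart one level lower (from 160 mg to 120 mg under Table 1) | Stop |
| Grade 3 event, resolved to Grade 1 on day 10 | 7-day sentence: stop (10 > 7). 3-week sentence: not removed (10 < 21) | Restart | Restart |
| Grade 3 event in Cycle 3, recovered to Grade 2 | Keep holding | Keep holding | Restart |

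**Row 1** is the main conflict. The three instructions cannot all be followed.

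**Row 2** is a conflict within one paragraph. Reading the 3-week sentence as removal from the study, distinct from stopping drug, does not help: its override is for continued treatment at a lower dose, so it presupposes that drug is still possible after 7 days.

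**Row 3** is a plain mismatch of recovery threshold between text and table.

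Next, is there a sentence that ranks these rules?

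- The opening of Section 6.3 says where the guidelines are. It suggests that Table 6 is the reference, but not that the table overrides the paragraphs, each of which gives its own instruction.
- Section 6 says "Dose adjustments will be based on the organ system exhibiting the greatest degree of toxicity". That chooses between organ systems, not between two rules for one toxicity.
- Section 3.3 ends treatment for irreversible or intolerable toxicity, which does not settle an event that has resolved.
- Section 8.2 refers to the approved labelling without ranking text against table.

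None settles row 1. The neighbouring non-hematologic rules do indicate the likely intent. In Table 3 the row "Baseline Any Grade-Grade 4" stops regorafenib, and so does the Grade 4 row of Table 5; Table 4 has no Grade 4 row. As a general Grade 4 option, hold-and-restart otherwise appears only in Table 2, which is hematologic. Paragraph 2 is therefore the sentence out of line.

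**The case against.** The best defence is that a careful site would stop the drug anyway. Section 6.3 names Table 6 as the guideline, Table 6 stops for Grade 4, and paragraph 1 uses 'will' where paragraph 2 uses 'should'. The scope is narrow, and even paragraph 2 demands recovery to Grade 1 or less and a lower dose. Serious events reach the sponsor within 24 hours (Section 11.2), and the Medical Monitor reviews toxicity after the first 10 patients in each cohort (Section 10.4.3).

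This makes re-dosing less likely, but it does not remove the instruction to re-dose. Neither the notice nor the review tells the site what to do with the patient in front of it.

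Other parts of the defence stand. A reader might list the restart dose and the laboratory exceptions as conflicts of equal weight. The documents do not support that. Table 6 also restarts one level lower by default, and its Level 0 wording is an option the investigator may consider. The laboratory route and footnote b read as specific exceptions to a general stop. These need clearer drafting only. The missing time limit in Table 6 is arguably filled by Section 6.1, whose 3-week limit is worded for treatment-related toxicity although it sits under a hematologic heading.

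**Conclusion.** The Grade 4 instructions in Section 6.3 are wrong as written and should be corrected, because a site obeying paragraph 2 would re-dose after a Grade 4 event. The Grade 3 time limit and recovery threshold are real but secondary inconsistencies.

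The size of any effect is unknown. Two stronger inferences should be avoided.

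- A reader might count instructions: two of three in Section 6.3 stop for Grade 4, or four of five with Tables 3 and 5 added. That identifies the outlying sentence; it does not measure risk to patients.
- A reader might infer that the primary safety result is compromised. Section 10.4.4 bases safety on the incidence of treatment-emergent adverse events by cohort, Section 10.2 rules out formal testing, and no estimate or stopping rule is shown to change. The traceable consequence for the analysis is confined to the SAP's descriptive modification and discontinuation tables.

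The conclusion assumes that the Grade 4 stop is the intended rule, as paragraph 1, Table 6 and the neighbouring tables indicate.

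**What to change.** **Grade 4**

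1. In paragraph 2, delete 'or 4' from the hold-and-restart sentence.
2. In paragraph 1, add to the Grade 4 stop: *except as allowed in Table 6 and its footnote b*.
3. Have the sponsor confirm whether Grade 4 nausea or vomiting persisting after maximal antiemetics is an intended exception. If so, list it in Table 6; if not, delete 'or 4' from that sentence too.
4. State that Table 6 governs where text and table differ.

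**Grade 3**

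5. Delete the 7-day sentence. Keep the 3-week limit with the Medical Monitor override, which matches Section 6.1; say when the 3 weeks start and put the limit in Table 6 as well.
6. Use the same recovery threshold in the text and Table 6. The sponsor must choose the grade. If a cycle distinction stays, write it in terms of regorafenib cycles, because Cohort 2 first takes regorafenib in study Cycle 2.

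The restart-dose option can be clarified in the same edit.

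**Cost:** one text amendment. Section 13.1 lists risk to patient among the changes needing IRB approval; regulatory submission follows if applicable, with re-issue to about 5 sites. Dropping the 7-day sentence keeps some patients eligible to restart whom that sentence would stop. Choosing Grade 1 or less lengthens some holds relative to Table 6; choosing Grade 2 or less allows some earlier restarts than the text permits. No sample size or planned analysis changes.

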6.1 Dose Modifications Due to Hematologic Toxicity

Dose reductions or holds and initiation of supportive care are allowed as clinically indicated by the treating physician. Patients whose treatment is delayed due to toxicity will discontinue study drug or will proceed with the next cycle of treatment when toxicity has improved (as long as the toxicity resolves within 3 weeks) according to the dose modifications below. Two dose reductions for toxicity will be allowed. In addition, dose reductions will also be allowed based on clinical judgment of the treatment physician. If persistent toxicity occurs despite two dose reductions, the patient will be removed from the study.

Patients who require a treatment delay of more than 3 weeks due to treatment-related toxicity will be discontinued from study treatment, unless the treating physician and the Medical Monitor agree that continued treatment at lower doses is in the best interest of the patient.

Table 1 Regorafenib Dose Levels for Dose Modifications due to Toxicities

Dose Level	Regorafenib ^a
0	160 mg orally once daily
-1	120 mg orally once daily
-2	80 mg orally once daily

^a Two dose reductions are allowed for regorafenib. Patients who require more than two dose reductions due to toxicity will be discontinued from the study.

The regorafenib dose modifications for hematologic toxicities are below in Table 2.

CONFIDENTIAL

STUDY DEVICE: SIR-Spheres®

SCRI INNOVATIONS STUDY NUMBER: GI 189

DATE OF ORIGINAL PROTOCOL: 16 December 2013

Version 2.0

Date of Amendment #1: 15 April 2014

Table 2 Regorafenib Dose Modifications for Hematologic Toxicities

Toxicity	Regorafenib Dose ^a
Grade 3 And Recurrence of Grade 3	Hold dose until recovery to \leq Grade 2, then resume regorafenib at one lower dose level.
Grade 4	Hold dose until recovery to \leq Grade 2, then resume regorafenib at one lower dose level, or discontinue at the discretion of the investigator after discussion with the Medical Monitor.

^a Any patient who requires a treatment delay of more than 3 weeks due to treatment-related toxicity will be discontinued from study treatment, unless the treating physician and the Medical Monitor agree that continued treatment at lower doses is in the best interest of the patient.

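### Section 6.3 gives conflicting orders on stopping or resuming regorafenib after Grade 4 and prolonged Grade 3 non-hematologic toxicity, and does not say which rule governs

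*Protocol*

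**What the plan says.** Section 6.3 covers regorafenib-related non-hematologic toxicity that has no table of its own. Liver tests, hand-foot skin reaction and hypertension are handled in Tables 3 to 5. The section opens with a pointer, "The dose reduction guidelines for non-hematologic toxicities are shown in Table 6", and then sets out rules in two paragraphs before the table itself.

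- **First paragraph, Grade 3.** Where the toxicity is expected to be manageable and reversible with a lower dose, hold until Grade 1 or better. Then: "If the Grade 3 non-hematologic toxicity lasts longer than 7 days, study drug will be discontinued". The next sentence removes patients whose Grade 3 toxicity lasted 7 days or more and has not reached Grade 1 or better within 3 weeks, "unless the treating physician and the Medical Monitor agree that continued treatment at lower doses is in the best interest of the patient".
- **First paragraph, Grade 4.** "If a Grade 4 non-hematologic toxicity occurs, study drug will be discontinued".
- **Second paragraph.** "If Grade 3 or 4 non-hematologic toxicity other than nausea, vomiting, or alopecia occurs, treatment with regorafenib should be held, and should be resumed" one level lower once it is Grade 1 or better. For nausea and vomiting, the reduction applies only if Grade 3 or 4 persists for 7 days despite maximal antiemetic prophylaxis.
- **Table 6, Grade 3.** Hold to Grade 2 or better (Grade 1 or better for events in Cycle 1), then resume one level lower. "For AEs occurring in Cycle 2 or later the investigator may consider a retreatment at the dose Level 0". There is no time limit.
- **Table 6, Grade 4.** Discontinue, except that certain laboratory toxicities are decided between investigator and sponsor. Footnote b separately lets some lipase, amylase and phosphate abnormalities continue without a hold.

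Section 6.1, under its hematologic heading, has a general 3-week rule with a Medical Monitor exception: "Patients who require a treatment delay of more than 3 weeks due to treatment-related toxicity will be discontinued from study treatment".

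**The concern.** A dosing section has to give a site one answer for one event. Here two adjacent paragraphs give opposite orders for Grade 4, and two adjacent sentences give different limits for Grade 3. The table then differs from the text on how far the patient must recover and at what dose to restart. The pointer to Table 6 does not say that the table overrides the text.

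Safety is the primary objective. Patients with severe toxicity could be taken off regorafenib or re-exposed to it depending on which sentence a site reads. The same choice feeds the summary of adverse events leading to treatment discontinuation (Protocol 10.4.4) and the SAP's tables of regorafenib modifications and treatment discontinuations with reasons.

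**Working it through.** The plan states no figure to reproduce, so the check is to set the rules side by side on test cases. The dose inputs are from Table 1 (Level 0 = 160 mg daily, Level -1 = 120 mg daily) and Section 5.1 (21 dosing days per cycle).

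**(a) Grade 4, other than nausea, vomiting or alopecia, in a patient on 160 mg.**
- First paragraph: discontinue. Next course = 0 mg.
- Second paragraph: hold, then resume at Level -1 after recovery. Next full course = 120 x 21 = 2,520 mg.
- Table 6: discontinue, unless the laboratory exception is used.

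Two of the three sources agree. The second paragraph cannot be reconciled with the first.

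**(b) Grade 3 for 10 days, resolved to Grade 1 by day 15.**
- 7-day sentence: stop, because 10 > 7.
- 3-week sentence: no removal, because resolution came within 21 days. The second paragraph then resumes one level lower.
- Table 6: no duration stated.

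The two limits are 21 - 7 = 14 days apart. If the 7-day sentence is applied strictly, the drug has already been stopped for every event over 7 days. The 3-week sentence is then left with only the event in which Grade 3 lasted exactly 7 days, and its exception, which contemplates further dosing, has almost nothing to act on. Tables 2, 4 and 5 each carry a delay limit in a footnote (3, 3 and 4 weeks), so the gap in Table 6 does not follow the pattern of those tables.

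**(c) Grade 3 for 4 days, then Grade 2, in Cycle 2 or later.**
- Text: keep holding to Grade 1, then 120 mg. Full course = 2,520 mg.
- Table 6: may resume at Grade 2. The default is 120 mg (2,520 mg), with 160 mg at the investigator's option (160 x 21 = 3,360 mg).

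The difference is one recovery grade plus an optional 3,360 - 2,520 = 840 mg, and 840 / 3,360 = 25% of the full dose. A site that waits for Grade 1 and restarts at 120 mg satisfies both. Table 6 also lacks the text's separate treatment of nausea, vomiting and alopecia.

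**Cycle labels (secondary).** Cohort 1 takes regorafenib in Cycle 1. Cohort 2 receives only SIR-Spheres in Cycle 1 and starts regorafenib on Cycle 2 Day 1 (7.4.2, 7.4.4, Appendix B). Read literally, Table 6's stricter Cycle 1 clause therefore never reaches Cohort 2. In the first regorafenib cycle after SIR-Spheres (Cohort 1 Cycle 3, Cohort 2 Cycle 2), the literal table treats both cohorts alike.

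**The case against.** The strongest defence is that Table 6 says nothing about duration, and silence is not an order to resume after any delay. A site may hold as the table says and stop when a limit in the text is reached, breaching neither. This stands. A reader might infer that, for Grade 3 beyond 7 days, the text stops the drug while the table restarts it. The documents do not support that contrast, nor a milligram difference built on it: the table is silent on duration, and the text's own 3-week sentence leaves room to resume. The firm conflict over duration lies within the text.

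A softer defence takes the 7-day sentence as ending the drug and the 3-week sentence as ending study participation. It fails because the exception in the latter is for continued treatment.

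A reader might also infer from the cycle labels that the cohorts are meant to be managed differently, biasing their comparison. That is not supported either. Sections 5, 5.2 and 7.5 speak of cycles of regorafenib, and footnote g on Coumadin monitoring was renumbered from Cycle 1 in Appendix A to Cycle 2 in Appendix B. Table 6 is most likely a label that was not adapted, with a small effect.

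Finally, the reach is limited. The stopping rules and the adverse event table by grade count the index event before any restart rule applies, the restart at 160 mg is discretionary, and footnote b takes some laboratory events out. All of this stands. None of it resolves Grade 4 or the 7-day versus 3-week sentences.

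**Conclusion.** The conflict is real and should be corrected. It has two firm parts: opposite orders for Grade 4, and two incompatible time limits for Grade 3 within the same paragraph. A milder third part, on recovery grade and restart dose, can be met by a cautious site. The cycle labels are a secondary drafting point.

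For one Grade 4 event at 160 mg, the size is 0 versus 2,520 mg over the next full 21-day course, assuming recovery to Grade 1 and no laboratory exception. For the restart rule it is one recovery grade and an optional 840 mg. How many of the 50 patients would meet these rules cannot be said, because the documents give no event rates for residual non-hematologic toxicity.

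The consequence is for patient safety and for descriptive tables of dose modification and discontinuation. Section 10.2 plans no hypothesis test, so no error rate or sample-size figure changes.

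**What to change.** Amend Section 6.3 as follows.

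1. **Grade 4.** Remove Grade 4 from the hold-and-resume sentence, so that it is discontinued as in the first paragraph and Table 6, keeping the table's laboratory exception. The nausea and vomiting sentence that follows also names Grade 4 and needs the same decision.
2. **Time limit.** Replace the 7-day and 3-week sentences with one limit. The natural default is the 3-week limit with Medical Monitor exception already used in 6.1. Repeat it as a footnote to Table 6. Stating only that Table 6 prevails would not be enough, because the table has no limit.
3. **Recovery and restart.** Use one recovery grade, one restart dose and one set of nausea, vomiting and alopecia exceptions in both text and table.
4. **Labels.** In Table 6, refer to the first regorafenib cycle and to later regorafenib cycles. State which rule applies to the first regorafenib cycle after SIR-Spheres in each cohort. Relabelling alone would make Cohort 2 Cycle 2 strict and leave Cohort 1 Cycle 3 lenient, so that should be a deliberate choice.

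The clinical team should confirm the grade, dose and limit. The cost is a short amendment to two paragraphs, the Grade 3 row and a footnote, with no added visits or data.
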